## **5.2. Safety**

To evaluate the safety of automated closed-loop glucose control in terms of episodes and severity of hypoglycaemia and nature and severity of other adverse events.

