# **9. Study Schedule**

## **9.1. Overview**

The study will be coordinated from the Institute of Metabolic Science, University of Cambridge, and performed at the following sites

1. Addenbrooke's Hospital, Cambridge, UK
2. Manchester Royal Infirmary, Manchester, UK
3. Queen Elizabeth Hospital, Birmingham, UK
4. Medical University of Graz, Graz, Austria

The study will consist of up to 19 visits or pre-planned telephone/email contacts including two study periods (closed-loop vs. sensor-augmented pump therapy). The study periods will last 4 months each. The order of the two interventions will be in random order.

The visit to set up automated closed-loop for the first time may take place in the study or clinical facility or can be done remotely. All other visits can take place at the hospital clinic, home or other suitable meeting place or remotely, according to participants' convenience. Two 16-week study periods will be performed within four weeks of each other. Maximum time in study is 12 months.

Table 1 outlines study activities when CL intervention precedes sensor-augmented pump therapy.

Table 2 outlines study activities when sensor-augmented pump therapy precedes CL intervention.

*Table 1. Schedule of study visits when closed-loop intervention precedes sensor-augmented pump therapy.*

	Visit/ contact	Description	Start relative to previous / next Visit / Activity	Duration
	*Visit 1	Recruitment visit: Consent HbA1c, baseline bloods, 12-lead ECG, human factor assessment	-	1-3 hours
Study Pump & CGM Training /Run-In	*Visit 2	Insulin pump training and initiation of study pump Competency assessment	Can be combined with Visit 1, or within 1 to 3 weeks of Visit 1	3-4 hours
	*Visit 3	CGM training Initiation of CGM Competency assessment	Within 7 days of Visit 2. Can coincide with Visit 2	1 hour
	*Visit 4	Review pump and CGM data & compliance assessment & Randomisation	After 3 - 4 weeks of Visit 3	1-2 hours
CL Intervention (4 months)	*Visit 5	CL initiation at CRC or remotely - CL training & competency assessment - HbA1c	Can be combined with Visit 4, or within 2 week of Visit 4	Up to 6 hours
	* Visit 6	Review use of study devices	After 24-48 hours of Visit 5	<1 hour
	*Visit 7	Review use of study devices	After 1 week of Visit 5	<1 hour
	*Visit 8	Review pump and CGM data	After 1 week of Visit 7	<1 hour
	*Visit 9	End of first month; Review pump and CGM data.	After 4 weeks of Visit 5	<1 hour

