	*Visit 16	End of second month; Review of home data. Actiwatch sleep monitor	After 4 weeks of Visit 15	<1 hour
	*Visit 17	End of third month. Review of home data.	After 4 weeks of Visit 16	<1 hour
	*Visit 18	12-lead Holter monitor applied for 5 days.	Within 14 days after Visit 17. Can coincide with Visit 17	<1 hour
	*Visit 19	End of open-loop treatment period (4 months) HbA1c. Revert back to usual pump therapy. Human factor assessment	After 4 weeks of Visit 17	1-2 hours
	-	Washout period	Immediately after Visit 19	4 weeks

CL Intervention (4 months)	*Visit 5	CL initiation at CRC or remotely - CL training & competency assessment - HbA1c	After 4 weeks of end of Visit 19	Up to 6 hours
	* Visit 6	Review use of study devices	After 24-48 hours of Visit 5	<1 hour
	*Visit 7	Review use of study devices	After 1 week of Visit 5	<1 hour
	*Visit 8	Review pump and CGM data	After 1 week of Visit 7	<1 hour
	*Visit 9	End of first month; Review pump and CGM data.	After 4 weeks of Visit 8	<1 hour
	*Visit 10	End of second month; Review pump and CGM data. Actiwatch sleep monitor	After 4 weeks of Visit 9	<1 hour
	*Visit 11	End of third month; Review pump and CGM data.	After 4 weeks of Visit 10	<1 hour
	*Visit 12	12-lead Holter monitor applied for 5 days.	Within 14 days after Visit 11. Can coincide with Visit 11	<1 hour
	*Visit 13	End of closed-loop treatment period (4 months). HbA1c. Collect algorithm device. Revert back to usual pump therapy. Human factor assessment.	After 4 weeks of Visit 11	1-2 hours

\*Could be done via phone / e-mail in UK.

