## **9.18. End of control treatment (Visit 19)**

The subject will be invited to attend the research centre approximately 4 weeks after Visit 17. If required this visit can be done remotely by telephone. This would be the end of the study period and subjects will return to their normal diabetes care. Insulin pump will be downloaded. The subject will have a blood test (capillary/venous) for the HbA1c. A human factors survey assessment (Table 3) will be performed. Participants will be invited to a focus group for investigators to gather feedback and reactions to the closed-loop system, the clinical trial, and quality of life changes.

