## **11.2. Recording and Reporting of Adverse Events, Serious Adverse Events and Device Deficiencies**

### **11.2.1. Monitoring Period of Adverse Events**

The period during which adverse events will be reported is defined as the period from the beginning of the study (obtaining informed consent) until 3 weeks after the end of the second intervention. Adverse events that continue after the subject's discontinuation or completion of the study will be followed until their medical outcome is determined or until no further change in the condition is expected. The follow up of AEs may therefore extend after the end of the clinical investigation; however no new AEs will be reported after the trial reporting period.

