225 **7.9 Sleep Analyses**

226 The Pittsburgh Sleep Quality Index (PSQI) and actigraphy data will be used to calculate mean
227 total sleep quality score, sleep duration, time in bed, sleep disturbance (including wake after
228 sleep onset and number of awakenings), latency, efficiency, quality, and daytime dysfunction.

229 Sleep will be automatically scored by Actiware software using previously described and
230 validated algorithms. Sleep duration will be calculated as the sum of all epochs scored as sleep
231 during the time in bed. Variability across nights in a participant's sleep duration will be
232 summarised using the coefficient of variation. Sleep data will be averaged across nights in each
233 participant for each study period. The analysis will be conducted by [name]

234 **7.10 Holter Data Analyses**

235 Holter monitor data at the fourth month in the two treatment groups will be analysed at the end
236 of the study. Arrhythmic events analysed will include atrial fibrillation, atrial ectopic beats,
237 bradycardia, ventricular premature beats, complex ventricular premature beats, non-sustained
238 ventricular tachycardia and measures of heart rate variability and QT interval. All identified
239 arrhythmic events will be manually verified for accuracy.

240 Investigators will be masked to glucose values during arrhythmia analysis. The frequency of
241 arrhythmic events during periods of hypoglycaemia (sensor glucose ≤ 3.9 mmol/L and 3.0
242 mmol/L), will be compared to the frequency of arrhythmic events during normoglycaemia (3.9-
243 10 mmol/L) within each study arm. Analyses will be calculated for daytime and night-time
244 periods to take into account diurnal variation. Any incidental finding will be referred by the
245 Investigator to the clinical team and be managed as per local site policy.

246

247 **8. Safety Analyses**

248 All safety outcomes will be tabulated by participant for all events from enrollment to the final
249 study visit.

250 **8.1 Definitions**

251 Reportable adverse events for this protocol include any untoward medical occurrence,
252 unintended disease or injury, or untoward clinical signs (including abnormal laboratory findings)
253 in a subject who has received an investigational device, whether or not related to the
254 investigational medical device. These include severe hypoglycemia (SH) and diabetic
255 ketoacidosis (DKA).

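### The SAP's safety tabulation stops at the end of period 2, three weeks before the protocol's adverse event window closes, and the SAP does not say whether or how events in that gap are listed

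*SAP*

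**What the plan says.** Protocol 11.2.1 opens the adverse event period at consent and keeps it open "until 3 weeks after the end of the second intervention". It then closes it: "no new AEs will be reported after the trial reporting period". The three weeks are therefore part of the planned reporting window.

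SAP section 8 begins: "All safety outcomes will be tabulated by participant for all events from enrollment to the final" study visit.

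The visit schedule fixes when that final visit occurs. Protocol 9.1 states: "The study will consist of up to 19 visits or pre-planned telephone/email contacts". Tables 1 and 2 show none after the end of the second treatment period.

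- **Closed loop first:** the last visit is Visit 19. Protocol 9.18 says of it: "This would be the end of the study period and subjects will return to their normal diabetes care".
- **Control first:** the last visit is Visit 13, the end of closed-loop treatment, where Table 2 has: "Collect algorithm device. Revert back to usual pump therapy".

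Two further parts of the SAP bear on the point. Section 8.2 provides for listing every severe hypoglycaemia, DKA and other reportable event by treatment group, with separate listings before and after randomisation, and states no end date. Section 8.3 defines each safety period as initiation visit to end-of-treatment visit. It names two kinds of event to be kept out of rates and comparisons: those before initiation in period 1 and those in the washout.

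**The concern.** The two documents give different end dates for safety data, and the difference is the whole three-week tail. The protocol chose to keep reporting open for those weeks, but the opening rule of the SAP's safety section stops before they begin.

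The tail is also when participants change treatment. Under Protocol 9.22 they do not keep the study devices and go back to their conventional pump therapy. With 1:1 allocation of sequence, about half (those on control first) come directly off closed loop at that visit. A severe hypoglycaemia or DKA event soon afterwards would be reportable under the protocol. An analyst following SAP 8 literally would leave it out of the tabulated safety results. An analyst relying on SAP 8.2 might list it, but would have no rule for the treatment group to assign. What is at stake is the completeness and consistent labelling of the safety report, not the comparison of treatments.

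**Working it through.** The plan states no figure for this gap, so there is none to reproduce. The check compares two windows and then sizes the difference.

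**Step 1: end dates**

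| Item | Closed loop first | Control first |
|---|---|---|
| End of second intervention | Visit 19 | Visit 13 |
| Last scheduled contact | Visit 19 | Visit 13 |
| End of SAP 8 window | Visit 19 | Visit 13 |
| End of Protocol 11.2.1 window | Visit 19 + 21 days | Visit 13 + 21 days |

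The windows would agree only if a visit took place three weeks after treatment. None is scheduled, so the gap is 21 days for each participant who completes period 2.

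**Step 2: which events are affected**

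- Washout events follow the end of period 1 and precede the final visit. They are inside the SAP 8 window, and SAP 8.3 keeps them out of rates and comparisons only.
- Events after the second end-of-treatment visit are outside the SAP 8 window. SAP 8.3 does not name them among its exclusions, but its period definition already keeps them out of the rates.
- SAP 8.2 could be read as including them, since they occur after randomisation and the section has no cut-off. It could equally be read as governed by the opening sentence of section 8, which covers all safety outcomes. Neither reading settles which treatment group such an event belongs to.

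**Step 3: size of the gap**

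Inputs: 36 participants (SAP section 3); 21 days (Protocol 11.2.1); two periods of 112 days (16 weeks each; SAP 4.1 uses 112 days). All 36 are assumed to complete period 2.

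- Gap person-time = N × 21 / 365.25 = 36 × 21 / 365.25 = 2.07 person-years.
- On-treatment person-time = N × 2 × 112 / 365.25 = 36 × 224 / 365.25 = 22.08 person-years.
- Ratio = 2.07 / 22.08 = 9.4%.

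With 31 completers (the number required by the power calculation in Protocol 14.6) the gap is 1.78 person-years. With 42 (the recruitment ceiling in the synopsis) it is 2.41. The ratio stays at about 9.4% because N cancels.

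**Step 4: effect of extending the window**

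The tabulation gains 21 days per completer. Rates, person-year denominators and model comparisons under SAP 8.3 do not change.

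**The case against.** The strongest reply is that little is lost. SAP 8.2 lists all episodes with no end date, and an event in the tail is plainly after randomisation. Protocol 14.5 likewise tabulates severe hypoglycaemia and ketone-positive hyperglycaemia for all subjects without a cut-off. Serious events, which include severe hypoglycaemia and DKA, go to the sponsor within 24 hours, and the DSMB is informed whatever SAP 8 says. No rate or test moves, and nobody is on a randomised treatment during those weeks.

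Most of this stands, and it limits the point. A reader might infer that every tail event is certain to appear in no table or listing. The documents do not support that, because SAP 8.2 can be read as including them. What remains is that the one explicit window in the SAP excludes these events while the listings leave their inclusion and treatment label open. Oversight during the trial does not settle what the final report contains.

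A reader might also infer that events at every switch off closed loop are lost. They are not: participants on closed loop first come off it into the washout, which is inside the window.

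Finally, a reader might multiply 2.07 person-years by the background figure of one severe episode per patient-year in Protocol section 4 and expect about two missed events. That figure describes the average patient with type 1 diabetes, whereas this trial excludes anyone with more than one severe episode in the preceding six months (Protocol 7.1.2). Under Protocol 11.2.2, adverse events are elicited at visits, and none falls in the tail. Spontaneous reports would be recorded, but the 2.07 person-years are not equivalent to monitored follow-up.

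**Conclusion.** The mismatch is real and should be corrected before analysis. The SAP 8 window ends 21 days before the protocol's reporting period for each participant who completes period 2. That is about 2.1 person-years for 36 completers (1.8 to 2.4 for 31 to 42), or 9.4% of on-treatment person-time. Within the gap, reportable events fall outside the stated tabulation, and their place in the SAP 8.2 listings is ambiguous.

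The scope is limited to the time after period 2. The primary endpoint, the on-treatment safety rates and the treatment comparisons are unaffected. No expected number of events can be given with any confidence. The conclusion assumes that the final study visit means the last visit in Tables 1 and 2, which is the only reading the schedule offers for completers.

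**What to change.** 1. In SAP section 8, change the window so that it runs from enrollment "until 3 weeks after the end of the second intervention", in line with Protocol 11.2.1.
2. In SAP 8.2, state that events after the second end-of-treatment visit are listed separately as post-treatment events, by the last treatment received.
3. Leave the rates, person-year denominators and comparisons in SAP 8.3 unchanged.
4. Label the new listing as based on reported events, because no contact is scheduled in those three weeks and the listing cannot be presented as systematic elicitation.

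The cost is a wording change in two SAP sections and one extra listing. The protocol already makes these events reportable, so no new data requirement or protocol amendment is needed. The small downside is that reporting in the tail may be less complete than reporting at visits, which the label in step 4 makes plain.

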### **11.2.3. Severe Hypoglycaemia**

Severe hypoglycaemia will be defined as an event requiring assistance of another person to actively administer carbohydrate, glucagon, or other resuscitative actions. These episodes may be associated with sufficient neuroglycopenia to induce seizure or coma. If plasma glucose measurements are not available during such an event, neurological recovery attributable to the restoration of plasma glucose to normal is considered sufficient evidence that the event was induced by a low plasma glucose concentration.

Severe hypoglycaemia will be regarded as a foreseeable serious adverse event and a serious adverse event form will be completed. Non-severe hypoglycaemia will not be reported or considered an adverse event.

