### **11.2.4. Hyperglycaemia, Ketonaemia and Diabetic Ketoacidosis**

Diabetic Ketoacidosis (DKA) is defined as: hyperglycemia (blood glucose >250 mg/dl or >13.9 mmol/l) with low serum bicarbonate (<15 mEq/l) and/or low pH (<7.24), anion gap (> 12) and either ketonemia or ketonuria and requiring treatment within a health-care facility (American Diabetes Association Workgroup on Hypoglycemia, Diabetes Care 28:1245-1249, 2005).

DKA will be regarded as a foreseeable serious adverse event and a severe adverse event form will be completed.

Severe hyperglycaemic events (fingerprick glucose >300 mg/dl/16.7mmol/l and blood ketones >0.6mmol/l) will be recorded as Adverse Events. Non-severe hyperglycaemia events will not be reported or considered as adverse events.

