### **11.3.2. Hypoglycaemia and hyperglycaemia**

Subjects with type 1 diabetes have a pre-existing risk for hypoglycaemia and hyperglycaemia. Potential risks are:

- Risk of mild to moderate hypoglycaemia and associated symptoms such as sweating, trembling, difficulty thinking and dizziness. There is also a rare risk of severe hypoglycaemia when conscious level is altered, needing help from a third party to correct the hypoglycaemia. These risks are pre-existent in any patient with type 1 diabetes and the study objective is to develop systems to minimise these risks
- Risk of possible mild to moderate hyperglycaemia similar to the risk that a subject with type 1 diabetes experiences on a daily basis
- Risk of hyperglycaemia leading to diabetic ketoacidosis (DKA). This risk is pre-existent in any patient with type 1 diabetes.

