256 Hypoglycemic events will be considered severe if the event requires assistance of another person
257 due to altered consciousness to actively administer carbohydrate, glucagon, or other resuscitative
258 actions. If plasma glucose measurements are not available during such an event, neurological
259 recovery attributable to the restoration of plasma glucose to normal is considered sufficient
260 evidence that the event was induced by a low plasma glucose concentration.

261 Definite DKA is defined as having all of the following:

262 • Hyperglycemia (blood glucose >11 mmol/L)
263 • with either low pH (<7.3) or low serum bicarbonate (<15 mmol/L)
264 • and ketonemia or ketonuria

265
266 **8.2 Adverse Events Summary**

267 All episodes of SH and of DKA along with any other reportable adverse events will be listed by
268 treatment group.

269 Separate listings will be provided for pre-randomization and post-randomization adverse events.

270 **8.3 Comparison of Safety Outcomes between Treatment Groups**

271 The following safety analyses will be performed if enough events occur for formal statistical
272 analyses.

273 For each of the following safety outcomes, mean \pm SD or summary statistics appropriate to the
274 distribution will be tabulated by treatment group:

275 • Number of subjects with any DKA events
276 • Number of episodes of DKA events per subject and incidence rate per 100 person years
277 • Number of subjects with any SH events
278 • Number of episodes of SH events per subject and incidence rate per 100 person years
279 • Number of adverse events per subject

280 • Number of serious adverse events per subject

281 All of the above safety outcomes will be tabulated for all subjects (including dropouts and
282 withdrawals), regardless of whether CGM data are available or whether the closed loop system
283 was operational (if the event occurred during the CL period). Any adverse events that occurred
284 before the treatment initiation visit in period 1 or during the washout period will not be included
285 in the rate calculations or treatment group comparisons listed above. In all safety analyses, each
286 period will inclusively consist of all days in between the treatment initiation visit and the end of
287 treatment visit.

288 The number of person-years for the incidence rate calculations in each period will be inclusively
289 defined as the number of person-years in between the treatment initiation visit date and the end

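### SAP 8.1 counts severe hypoglycaemia on narrower criteria and DKA on wider criteria than the protocol, and SAP 8.3 omits ketone-positive hyperglycaemia and makes its safety tables conditional on event numbers

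*SAP*

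**What the plan says.** **Severe hypoglycaemia (SH).** The operative definition is in protocol 11.2.3: "Severe hypoglycaemia will be defined as an event requiring assistance of another person to actively administer carbohydrate, glucagon, or other resuscitative actions". That section adds that neuroglycopenia may accompany such episodes but does not require it. It also fixes the recording route: "Severe hypoglycaemia will be regarded as a foreseeable serious adverse event and a serious adverse event form will be completed". SAP 8.1 has nearly the same sentence with one more condition, that the assistance was needed "due to altered consciousness to actively administer carbohydrate, glucagon, or other resuscitative" actions.

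**DKA.** Protocol 11.2.4 requires "hyperglycemia (blood glucose >250 mg/dl or >13.9 mmol/l) with low serum bicarbonate (<15 mEq/l) and/or low pH (<7.24), anion gap (> 12"), together with "either ketonemia or ketonuria and requiring treatment within a health-care facility". SAP 8.1 requires "Hyperglycemia (blood glucose >11 mmol/L"), then "with either low pH (<7.3) or low serum bicarbonate (<15 mmol/L"), plus ketones in blood or urine. It has no anion gap condition and no treatment-setting condition.

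**Ketone-positive hyperglycaemia.** Protocol 10.2 names severe hyperglycaemia (fingerprick glucose above 16.7 mmol/l with ketones above 0.6 mmol/l) as a safety outcome separate from DKA, and protocol 11.2.4 has it recorded as an AE. Protocol 14.5 commits to tabulating SH and ketone-positive hyperglycaemia in each treatment group, for all subjects including those who drop out. Only the comparison, by repeated measures logistic regression, depends on there being enough events. SAP 8.3 lists DKA, SH, AEs and SAEs and nothing else. Its event-rate model covers DKA and SH only, and its opening sentence makes everything that follows, tables included, depend on enough events.

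**The concern.** Sites classify and report SH and DKA under the protocol, while the SAP would count them on other criteria. An event with an SH form could be absent from the SH count, and an episode that is not DKA under the protocol could be counted as DKA. The SAE report contents in protocol 11.2.5 include an event description but no item on consciousness. Applying the SAP wording for SH would therefore mean reclassifying from narratives in an open-label trial, and the documents describe no masked adjudication of SH or DKA.

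Safety is a stated objective, and the protocol Summary asks whether closed-loop is safer as well as more efficacious. The planned safety tables should follow the definitions used to collect the events, and should include each outcome the protocol says will be tabulated.

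**Working it through.** The plan gives no figure to reproduce here. The check compares definitions, with one scale calculation.

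**1. SH.** Protocol rule: assistance from another person. SAP rule: assistance from another person and altered consciousness as the reason. Every SAP event meets the protocol rule. An assisted event without altered consciousness meets the protocol rule only. So SAP SH count ≤ protocol SH count.

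**2. DKA.**

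| Condition | Protocol 11.2.4 | SAP 8.1 |
|---|---|---|
| Glucose (mmol/l) | >13.9 | >11 |
| pH | <7.24 | <7.3 |
| Bicarbonate | <15 mEq/l | <15 mmol/L (same limit) |
| pH and bicarbonate joined by | and/or | or |
| Anion gap | >12 | none |
| Ketones, blood or urine | required | required |
| Treatment in a health facility | required | none |

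Since 13.9 > 11 and 7.24 < 7.3, and the remaining differences are extra protocol conditions, every protocol DKA meets the SAP rule. The reverse fails: glucose 12 mmol/l with pH 7.28 and ketones is DKA under the SAP only. So SAP DKA count ≥ protocol DKA count. If the anion gap were read as descriptive rather than required, the SAP rule would still be wider on glucose, pH and setting. Units do not explain the gap: 250/18.016 = 13.9 mmol/l, while 11 × 18.016 = 198 mg/dl.

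**3. Can the wider SAP definition be ascertained?** Protocol 11.2.4 says non-severe hyperglycaemia will not be reported as an AE. The example in step 2 is below the 16.7 mmol/l limit and is not protocol DKA, so neither specific form need exist for it. Protocol 11.1.2 excludes from recording only hyperglycaemia without significant ketonaemia, and the general SAE rules in 11.1.4 also apply, so some such episodes may still be on record.

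**4. Ketone-positive hyperglycaemia.** Protocol 14.5 does not define the term. Equating it with the severe hyperglycaemia with ketones above 0.6 mmol/l of protocol 10.2 is an inference, though a reasonable one. It is not in the SAP 8.3 list, and the SAP's logistic model for binary variables follows that list. Under the SAP it would appear only among AEs, in the 8.2 listing and the per-subject AE count.

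**5. Conditionality.** Protocol 14.5: table always, comparison when events suffice. SAP 8.3: table and comparison both only when events suffice.

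**6. Scale of one event.** Inputs: 36 planned subjects (protocol synopsis; SAP 3) and 16 × 7 = 112 days per period (SAP 4.1), assuming all 36 complete both periods.
- Person-years per treatment: 36 × 112/365.25 = 11.04
- One event: 100/11.04 = 9.06 per 100 person-years
- One subject in the proportion with any event: 1/36 = 2.8 percentage points
- With 31 completers (the required number in protocol 14.6): 31 × 112/365.25 = 9.51 person-years, and 100/9.51 = 10.5 per 100 person-years per event

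This is the granularity of a rate in a trial of this size. It does not estimate how many events would be reclassified.

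**The case against.** The strongest reply is that little would change in practice. An SH event that fails the SAP wording was still reported as an SAE, so it enters the per-subject SAE count in SAP 8.3 when that table is produced. SAP 8.1 defines reportable AEs broadly, so the event is also listed by treatment group under SAP 8.2. The opening of SAP Section 8 promises tabulation by participant for all safety outcomes. Ketone-positive events are in the AE listing and count. The protocol's own risk text in 11.3.2 speaks of "severe hypoglycaemia when conscious level is altered, needing help from a third party", which is close to the SAP wording. The SAP also calls its DKA category definite, which might suggest a deliberately separate category.

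Much of this stands as a limit on consequence. It does not remove the conflict. Section 11.3.2 describes risk, while 11.2.3 is the stated definition. The SAP defines no DKA category other than definite, so its counts have no other rule to use. A by-participant table and a general AE listing are not the by-treatment table that protocol 14.5 promises.

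A reader might infer that events would disappear from the report, or that the SAP wording favours closed-loop. The documents support neither. Recorded events keep a place under another label, the definitions apply equally in both treatment periods, and the two differences run in opposite directions.

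**Conclusion.** The inconsistency is real in all parts. SH is narrower and DKA wider in SAP 8.1 than in protocol 11.2.3 and 11.2.4. Ketone-positive hyperglycaemia is missing from SAP 8.3. SAP 8.3 also conditions its tables where protocol 14.5 conditions only the comparison. This should be fixed before analysis.

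The effect is limited. The number of reclassified events cannot be derived from the documents and may be zero. In practice the DKA counts may coincide, because episodes meeting only the SAP wording may not have been recorded. The primary and key secondary endpoints are not affected. With 36 completers one event is worth about 9.1 per 100 person-years, and more with fewer completers, so the classification of a single event would show in a reported rate. The ketone-positive part rests on the inference that protocol 14.5 and 10.2 mean the same event.

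**What to change.** Before analysis:

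- Reconcile SAP 8.1 with protocol 11.2.3 and 11.2.4 so that one definition of SH and one of DKA governs both site recording and the safety counts. This review takes no view on which clinical criteria are right.
- Check that the agreed wording stays consistent with protocol 9.19, where withdrawal criteria 5 to 7 also rest on SH and DKA.
- Report any count on the other wording as a labelled supplement.
- Add ketone-positive hyperglycaemia to the SAP safety tables by treatment, citing the protocol 10.2 criteria, with the protocol 14.5 logistic comparison when events suffice.
- Make the SH and ketone-positive tables unconditional, for all subjects, and keep only the model comparisons conditional. Adding a row under the present opening sentence of SAP 8.3 would not be enough, because with few events no table need be produced.

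The cost is SAP wording, one table row and one conditional model. Ketone-positive hyperglycaemia needs no new data, since protocol 11.2.4 already has it recorded. SH and DKA events already on file may need checking against the agreed wording. If reconciliation moves toward the SAP wording for DKA, AE and SAE records beyond the DKA forms must be searched, and the report should say that some qualifying episodes may never have been recorded.
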